6.6 Immunogenicity Analyses

All immunogenicity analyses will be performed with the PP population and repeated with the TV population. Descriptive summaries will be computed overall within group, and by site within group. In all cases, data from Groups 1 & 2 (for UAM4 and UAM1) will be combined prior to dose 2, as well as data from Groups 3 and 4 (UAM4).

6.6.1 Primary, Secondary, and Exploratory Immunogenicity Endpoints

Descriptive Analysis

For all time points where neutralizing antibody titers (NAbs) to polio serotype 2 are obtained, these will be summarized and displayed graphically (reverse cumulative distribution) by time point. Continuous-variable summary statistics will be computed and presented in tabular form for \log_2 NAbs and augmented with the GMT of antibody with accompanying 95% confidence intervals for both the GMT and median \log_2 titers. Confidence intervals for the median will be obtained using the percentile bootstrap method (n=10,000 replicates). Separately for each group and time point, the GMT will be computed in an intercept-only model using likelihood-based methods accounting for censoring, implemented in SAS PROC LIFEREG, using left- and right-censoring at assay LLOQ ($2.5 \log_2$) and ULOQ ($10.5 \log_2$), respectively, and a Normal error distribution assumption on the \log_2 scale and confidence intervals for the GMT will be obtained via reverse-transformation of the \log_2 mean and its corresponding two-sided 95% confidence intervals. For each post-baseline time point, the geometric mean fold rise (GMFR) will be computed via the \log_2 differences from baseline (and from prior visit, for two-dose recipients) with two-sided 95% confidence intervals based on the *t*-distribution, followed by the antilog transformation.

Seroprotection and seroconversion rates will be calculated for each time point (post-vaccination time points only for seroconversion), with accompanying 95% confidence intervals constructed using the Clopper-Pearson exact method. These binary endpoints will be further summarized corresponding to baseline serostatus. Seroconversion will additionally be computed among the subset of subjects where seroconversion was possible to observe (less than or equal to 4-fold from assay ULOQ at baseline).

Seroprotection rates at baseline will be accompanied by a two-sided Miettinen and Nurminen 95% confidence interval for the difference for Groups 1 & 2 combined as well as Groups 3 & 4 combined vs the UAM1 control (Group 1 & 2 combined). Similarly, comparisons of baseline seroprotection rate between Group 5 vs 7 and Group 6 vs 7 will be conducted. Comparison of baseline GMTs among these same groups will be conducted by computing the GMT ratio and corresponding two-sided 95% confidence interval obtained from modeling the \log_2 NAb titer as a function of group using SAS PROC LIFEREG, as described above. For IPV-vaccinated subjects, this will include a fixed effect for study site, utilizing SAS LSMEANS for pairwise comparisons. For by-site summaries, comparisons will only be available at the site in common between UAM4 and UAM1.

Comparative Analysis

The primary immunogenicity endpoint, seroprotection after a single dose of each vaccine candidate in OPV-vaccinated subjects, will be formally compared to the corresponding endpoint from UAM1 via a non-inferiority test of each of the novel candidates to the UAM1 Sabin 2 control, each using one-sided $\alpha = 0.025$ and a non-inferiority margin of -10%.

Secondary endpoints will be compared to corresponding endpoints from UAM1 in the same manner, using one-sided $\alpha = 0.025$ and considering margins of -10% for binary endpoints (seroconversion), and 2/3 for median antibody titer and GMT ratios. Non-inferiority margins for these secondary endpoints are not selected based on any specific criteria and are simply intended as benchmarks for unpowered comparisons.

In each case, non-inferiority comparisons will be conducted by computing the difference/ratio in endpoint between each candidate vaccine and the UAM1 Sabin 2 control (novel minus comparator), with corresponding two-sided $\alpha = 0.05$ confidence intervals, and comparing the lower confidence limit to the non-inferiority margin. Miettinen and Nurminen confidence intervals will be used for binary comparisons, asymptotic normal-based methods will be used for GMTs as described above using SAS PROC LIFEREG and incorporating a covariate for the baseline \log_2 NAb level, and bootstrap methods will be used for median titers and other continuous endpoints.

Immunogenicity among IPV-vaccinated subjects (Groups 5 through 7) will be summarized descriptively but will not be compared between groups.

The non-inferiority comparison of the primary immunogenicity endpoint (post-first-dose seroprotection rate) will be based on the combined data from each site in this study compared to the single-site data from the historical control study, UAM1, for OPV-vaccinated subjects. In order to assess any between-site differences within the current study (UAM4) and the ability to combine these in the comparison to the historical control, both seroprotection rate and GMTs will be compared between sites, within candidate vaccine arm (for OPV- and IPV-vaccinated groups):

- Both the pre-vaccination and post-vaccination seroprotection rates in UAM4 will be compared between sites by computing the two-sided 90% Miettinen and Nurminen confidence interval for the difference (corresponding to a two-sided level $\alpha = 0.10$ test). The pre-vaccination comparison will be made across all subjects in Groups 1 through 4, and also across all subjects within Groups 5 through 7. Post-vaccination comparisons will be made within vaccine candidate (within Groups 1 & 2, within Groups 3 & 4, within Group 5 and within Group 6). If 0 is not contained in the confidence interval for the post-dose-1 difference in seroprotection rate for either candidate in the OPV-vaccinated groups, comparisons for all immunogenicity endpoints will additionally be conducted among subjects only from the site in common between both studies. Additional investigations to identify the source of the differences may be conducted, e.g. subset comparison of seroprotection rates, seroconversion rates, and GMT ratios among those initially seronegative vs those initially seropositive to evaluate the role of differences in baseline immunity, and/or regression modeling.
- Between-site comparisons of GMTs will be based on a two-sided 90% confidence interval for the GMT ratio (corresponding to a two-sided level $\alpha = 0.10$ test), using SAS PROC LIFEREG to incorporate censoring at assay LLOQ and ULOQ, incorporating a covariate for baseline \log_2 NAb for post-baseline measurements, and using the antilog transformation for the \log_2 mean difference, as described above, and additionally assuming a common error variance among sites. As above, the pre-vaccination comparison will be made across all subjects in Groups 1 through 4, and separately across all subjects within Groups 5 through 7, while the post-vaccination comparisons will be made within vaccine candidate (within Groups 1 & 2, within Groups 3 & 4, within Group 5 and within Group 6). If the CI for the baseline-adjusted GMT ratio between sites post-dose-1 for either candidate among OPV-vaccinated subjects does not contain 1, the adjusted GMT ratio and corresponding CI for the GMT comparison of each candidate to the corresponding UAM1 control will additionally be conducted among subjects only from the site in common between both studies. Additional investigations to identify the source of the difference may be conducted.

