In the FIH study immune responses to both candidates were clearly evident, despite the high number of previously administered doses of IPV and the inability to detect a 4-fold rise in some participants due to baseline titers within 4-fold of the upper limit of quantitation for the assay. Only one participant did not have a seroprotective level of neutralizing antibodies to type 2 poliovirus at baseline (<1:8), and most participants demonstrated seroconversion (4-fold rise in antibody from baseline to 28 days post-vaccination). Median fold-rise in titer was 12.7 for Cohort 1 and 8.0 for Cohort 2.

This study is of major importance for global public health, contributing to the search of an improved OPV2 vaccine with less chance of reversion to neurovirulence.

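### Fold rise and median titer have no rule for values at the assay limits, so fold rise reads low and, if about 60% or more of a candidate arm is at ULOQ, median non-inferiority passes almost automatically

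*SAP*

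**What the plan says.** SAP 6.6.1 treats three summaries of the same titers in different ways.

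- **GMT.** Fitted in PROC LIFEREG "using left- and right-censoring at assay LLOQ ($2.5 \log_2$) and ULOQ ($10.5 \log_2$), respectively". The comparison with UAM1 follows suit: "asymptotic normal-based methods will be used for GMTs as described above using SAS PROC LIFEREG", with baseline log2 titer as a covariate.
- **GMFR.** "For each post-baseline time point, the geometric mean fold rise (GMFR) will be computed via the" log2 differences from baseline (and from the prior visit in two-dose recipients) "with two-sided 95% confidence intervals based on the *t*-distribution, followed by the antilog transformation". This is a complete-data method.
- **Median titer.** The descriptive interval is a percentile bootstrap. For the comparison with UAM1, "bootstrap methods will be used for median titers and other continuous endpoints", against a ratio margin of 2/3.

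Neither GMFR nor the median has a censoring method or a stated value for a titer at or beyond a limit. Protocol 10.1.3 likewise ties the likelihood method to GMTs only. The SAP does state substitution rules for safety laboratory values (6.5.2) and for shedding titers (6.7.1). For seroconversion it adds a subset analysis of subjects whose baseline leaves room for a 4-fold rise.

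Protocol 1.3.2 reports that in Phase 1 some participants could not show a 4-fold rise because of "baseline titers within 4-fold of the upper limit of quantitation for the assay".

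**The concern.** A titer above 10.5 log2 is known only to exceed 10.5. If it enters the GMFR as 10.5, the rise is understated. A baseline below 2.5 entered as 2.5 understates it as well. The size of the bias depends on the baseline titer, so UAM4 and UAM1 could show different fold rises for identical true responses, and SAP 5.1 has the two studies presented side by side.

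For the median the difficulty is identifiability. Once a capped median sits at ULOQ, the data say nothing about how far above it the true median lies. A bootstrap of capped values then reports a precise difference near zero, and a candidate worse than the SAP's own margin could be reported as non-inferior on a listed secondary endpoint.

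**Working it through.** The documents give no expected value, power or sample size for GMFR or for the median comparison, so there is no stated figure to reproduce.

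**Inputs from the documents.** L = 2.5 and U = 10.5 log2. Margin log2(2/3) = −0.585 (Protocol 10.1.3 writes it as 2/3 log2, which needs reconciling but does not change the mechanism). 100 subjects per candidate and 100 UAM1 controls at Day 28. Phase 1 median fold rises of 8.0 and 12.7.

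**Assumed.** Normal log2 titers, SD 1.5 to 2.5, baseline mean 4 to 8 log2, values beyond a limit entered at the limit.

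**Fold rise.** For mean μ and SD σ:

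- mean amount cut off above U: e(μ) = σ[φ(d) + dΦ(d)], d = (μ − U)/σ
- mean amount cut off below L: s(μ) = σ[φ(g) + gΦ(g)], g = (L − μ)/σ
- expected capped rise = true rise − e(post) + e(base) − s(base) + s(post)

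This does not depend on the within-subject correlation. With σ = 2 and a true rise of 3 log2 (8-fold):

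| Baseline mean | Post at ULOQ | Capped rise (log2) | GMFR |
|---|---|---|---|
| 6 | 23% | 3 − 0.262 + 0.008 − 0.032 + 0.000 = 2.71 | 6.6 |
| 7 | 40% | 3 − 0.573 + 0.032 − 0.008 + 0.000 = 2.45 | 5.5 |
| 8 | 60% | 3 − 1.073 + 0.101 − 0.002 + 0.000 = 2.03 | 4.1 |
| 4 | 4% (23% of baselines below LLOQ) | 3 − 0.032 + 0.000 − 0.262 + 0.008 = 2.71 | 6.6 |

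The last row is almost wholly an LLOQ effect. Over all the assumed values, for true 8.0 and 12.7, computed GMFR is 0.36 to 0.96 of the truth. Two studies with the same true 8-fold rise and baseline means of 6 and 7 would show 6.6 and 5.5, a ratio of 5.47/6.56 = 0.83. From Day 28 to Day 56 the bias is toward 1: with a Day 28 mean of 10, a true 2.0 reads 1.42 and a true 0.5 reads 0.62.

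**Median, threshold.** With n = 100 and k candidate titers at ULOQ, a resampled median equals ULOQ when at least 51 draws are at ULOQ. The number of such draws is Binomial(100, k/100). The chance of 50 or fewer is 0.027 for k = 60 and 0.016 for k = 61. From k = 61, therefore, the lower 2.5% bootstrap limit of the candidate median is ULOQ. A capped control median cannot exceed ULOQ, so the lower limit of the difference is at least 0, above −0.585, whatever the control titers are. The corresponding counts are 55 of 90 and 33 of 50.

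**Median, pass rates.** Simulated with SD 2, 100 per arm and a true ratio of 0.5 (−1.0 log2, worse than the margin):

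| Candidate at ULOQ | Control at ULOQ | Declared non-inferior | Without ceiling |
|---|---|---|---|
| 30% | 49% | 0.3% | 0% |
| 40% | 60% | 6% | 0% |
| 50% | 69% | 66% | 0.3% |
| 60% | 77% | 99.5% | 0% |

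Other runs, with different seeds and titer spacing, gave 0 to 10% at 40%, 36 to 74% at 50% and 93 to 100% at 60%. The transition moves a little, but the pattern does not.

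**Checking a repair for fold rise** (true 8.0, SD 2, correlation 0.5). The ratio of the two censored GMTs recovers 7.9 to 8.1. A censored-normal model fitted to the differences does not: it gives about 9 to 12, because the censoring point (10.5 − baseline) depends on baseline. Coding a below-LLOQ baseline as left-censored is worse still, since such a difference is right-censored: with baseline mean 4 it gives 4.8, against 6.6 from the plain method.

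**The case against.** A reader might infer that this trial's median comparison is bound to pass, or that any titers at ULOQ invalidate it. The documents support neither. Capping leaves a median unchanged while fewer than half of an arm is at the ceiling. The Phase 1 remark concerns some IPV-only vaccinated participants, most of whom still seroconverted, whereas the median comparison uses only OPV-vaccinated Groups 1 to 4.

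The planning assumption also points away from the extreme scenarios. With 95% at or above 1:8 (3 log2), normality and SD 2, the mean is 3 + 1.645 × 2 = 6.29 and about 2% exceed 10.5. The share is 20% at SD 3 and 41% at SD 4, and reaching 61% needs an SD near 5.5. But 95% is a planning figure and real titers may be skewed, so this makes the automatic pass less likely without excluding it.

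Much protection is already planned: a baseline-adjusted censored GMT ratio against UAM1 at the same 2/3 margin, reverse cumulative curves that show the share at ULOQ, and the seroconversion subset. SAP 6.6.1 says that the secondary margins have no specific basis and serve only as unpowered reference points. GMFR is a descriptive addition (SAP section 7).

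All of this stands and limits the consequence. It does not remove the gap. Lack of power warns of failing to show non-inferiority, not of a false pass, and no rule says which result governs if the median and the censored GMT ratio disagree.

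**Conclusion.** The point holds within limits. If titers beyond a limit are entered at the limit, GMFR from baseline is biased low, increasingly so with the share of post titers at ULOQ or baselines at LLOQ. For a true 8-fold rise at SD 2 it reads about 6.6, 5.5 and 4.1 with 23%, 40% and 60% at ULOQ. The difference in bias between studies can distort the display beside UAM1.

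The median comparison is reliable while clearly fewer than half of the candidate arm is at ULOQ, and close to an automatic pass from about 60%. Where this trial falls cannot be told from the documents. Titer means, SDs and correlation are all assumed here, and the substitution rule is inferred. The primary seroprotection conclusion is not touched.

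**What to change.** Amend SAP 6.6.1 before database lock.

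1. Derive GMFR as the ratio of the censored-likelihood GMTs at the two visits, with a confidence interval from a subject-level paired bootstrap or a joint model of both visits. Do not fit a censored model to the differences.
2. Report the percentage of titers at LLOQ and at ULOQ for each arm and time point, UAM1 included.
3. When the candidate median is at ULOQ, or a non-inferiority pass depends on a bootstrap limit that is at ULOQ, report the median comparison as not evaluable and draw the inference from the planned baseline-adjusted censored GMT ratio. Keep a failure to show non-inferiority when only the control arm is at the ceiling: capping the control can only favor the candidate, so that failure is informative.

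The cost is a few sentences and reuse of planned PROC LIFEREG code, with no new data. The downside is reliance on the normality assumption already made for GMTs, which carries more weight as the share at a limit grows. Setting the rule in advance also avoids choosing between the median and the GMT ratio after seeing the data.

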3.5.2 Secondary endpoints

Safety: The following endpoints will be evaluated by group and overall:

- incidence, type, causality and severity of solicited adverse events for days 0-7 in Groups 1 and 2 combined and days 28-35 in Group 2;
- incidence, type, causality and severity of solicited adverse events for days 0-7 in Groups 3 and 4 combined and days 28-35 in Group 4;
- incidence, type, causality and severity of solicited adverse events for days 0-7 and days 28-35 in Groups 5, 6 and 7;
- incidence, type, causality and severity of unsolicited adverse events throughout the study period in all groups;
- incidence, causality and description of deviations from normal safety labs at Day 0, Day 7, Day 14 and Day 28 for Groups 1 through 4, and at Day 35, Day 42 and Day 56 for Groups 2 and 4;
- incidence, causality and description of deviations from normal safety labs at Day 0, Day 7, Day 14, Day 28, Day 35, Day 42 and Day 56 for Groups 5, 6, and 7.

Immunogenicity:

- Median titers of type 2 polio antibodies at Day 28 in Groups 1 and 2 combined;
- Median titers of type 2 polio antibodies at Day 28 in Groups 3 and 4 combined;
- Median titers of type 2 polio antibodies at Day 28 in Groups 5, 6 and 7.
- Seroprotection rate and median titers of type 2 polio antibodies at Day 56 in Groups 2 and 4;
- Seroprotection rate of type 2 polio antibodies at Day 28 and at Day 56 in Groups 5, 6 and 7.
- Seroconversion rate of type 2 polio antibodies at Day 28 for Groups 1 and 2 combined and at Day 56 in Group 2;
- Seroconversion rate of type 2 polio antibodies at Day 28 for Groups 3 and 4 combined and at Day 56 in Group 4;

- Seroconversion rate of type 2 polio antibodies at Day 28 and at Day 56 for Groups 5, 6 and 7. Seroconversion is defined as a change from seronegative to seropositive and neutralizing antibody titers of $\geq 1:8$, and in seropositive subjects, as an antibody titer increase of ≥ 4 -fold over baseline titers.

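### SAP 6.6.1 inverts the definition of the subset in which seroconversion can be observed, so the supplementary seroconversion rate would be biased downward if programmed literally

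*SAP*

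**What the plan says.** Seroconversion is a secondary endpoint. SAP 3.5.2 defines it as moving from seronegative to seropositive with a titer of 1:8 or more and, "in seropositive subjects, as an antibody titer increase of" four times baseline or more. SAP 6.6.1 reports it for all subjects and by baseline serostatus. Under the descriptive analyses it then adds a further summary in the "subset of subjects where seroconversion was possible to observe (less than or equal to 4-fold from assay ULOQ at baseline").

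The same paragraph gives the assay limits where it describes the GMT model, "using left- and right-censoring at assay LLOQ ($2.5 \log_2$) and ULOQ ($10.5 \log_2$), respectively".

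Protocol 1.3.2, on the first-in-human data, describes the ceiling problem as "the inability to detect a 4-fold rise in some participants due to baseline titers within 4-fold of the upper limit of quantitation".

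SAP section 2 commits to performing every analysis that the SAP specifies. SAP 6.6 repeats the immunogenicity analyses in the per-protocol and total vaccinated populations and gives descriptive summaries by site. SAP section 7, which lists differences from the protocol, does not mention this subset.

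**The concern.** The extra summary exists to remove an assay artefact. A subject who starts close to the ULOQ cannot show a 4-fold rise, however strong the true response. The useful subset therefore leaves those subjects out. As worded, the rule keeps them and removes nearly everyone else. The SAP labels as observable the same group that the protocol gives as the reason a rise could not be detected.

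A programmer who follows the parenthesis would produce a rate far below the true one, and the error would carry into the tables for both populations and each site. The result need not be an obvious 0%. On a stepped titer scale it can look like a plausible low percentage, which is harder to notice. No other seroconversion summary separates subjects by distance from the ULOQ.

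**Working it through.** No sample size, power or alpha figure depends on this rule, so the plan has no figure of its own to reproduce. The check is arithmetic on the SAP's limits, followed by an illustration.

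**Inputs from the documents.** LLOQ is 2.5 log2 and ULOQ is 10.5 log2 (SAP 6.6.1). The rise needed in a seropositive subject is at least 4-fold, and log2(4) = 2 (SAP 3.5.2). I take a post-vaccination titer above the ULOQ to be recorded at the ULOQ.

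**Step 1: who can show the rise.** The largest recordable rise is 10.5 − baseline. A 4-fold rise is recordable when 10.5 − baseline ≥ 2, i.e. baseline ≤ 8.5 log2 (titer about 1:362 or lower).

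**Step 2: who the literal rule keeps.** Being no more than 4-fold away from the ULOQ means 10.5 − baseline ≤ 2, i.e. baseline ≥ 8.5 log2. The largest recordable rise is then 2^(10.5 − 8.5) = 4-fold at 8.5, 2^(10.5 − 9.5) = 2-fold at 9.5, and 2^0 = 1-fold (none) at 10.5. The two sets share only the value 8.5.

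**Step 3: count the levels.** The documents do not give the assay step, so four are assumed, each anchored at the LLOQ.

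| Assumed step (log2) | Levels kept by literal rule | Of these, 4-fold rise impossible | Levels where rise is possible | Of these, dropped |
|---|---|---|---|---|
| 0.25 | 9 | 8 | 25 | 24 |
| 1/3 | 7 | 6 | 19 | 18 |
| 0.5 | 5 | 4 | 13 | 12 |
| 1.0 | 3 | 2 | 7 | 6 |

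On every grid, baseline ≤ 8.5 matches the set where the rise is possible exactly.

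**Step 4: size of the bias (illustration).** Assumed, because the documents give no titer distribution: baseline log2 titer normal with mean 5 to 8 and SD 2; true rise normal with mean 3 and SD 1.5 log2; values limited to 2.5–10.5 and, on the stepped scales, rounded to the nearest level.

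| Titer scale | Literal rule, baseline mean 7 | Literal rule, baseline mean 8 | Correct subset, means 5 to 8 |
|---|---|---|---|
| Continuous | 0% | 0% | 75–77% |
| 0.25 step | 12% | 9% | 78–79% |
| 1/3 step | 16% | 12% | 78–80% |
| 0.5 step | 23% | 17% | 80–81% |
| 1.0 step | 40% | 32% | 84% |

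At baseline mean 5 the stepped scales give 18% to 54% under the literal rule. With continuous titers the all-subject rate is 58% at mean 7 and 45% at mean 8, and the literal subset holds 4% to 40% of subjects across means 5 to 8.

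**Step 5: hand check of one cell (0.5 step, mean 7).** Only the 8.5 level can contribute. It covers 8.25 to 8.75, so its share of the kept subjects is [Φ(0.875) − Φ(0.625)] / [1 − Φ(0.625)] = 0.0752/0.266 = 0.283. From 8.5, reaching the top level (10.25 or more before rounding) needs a rise of 1.75, with probability Φ((3 − 1.75)/1.5) = Φ(0.833) = 0.798. The product is 0.283 × 0.798 = 0.226, about 23%.

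**The case against.** The strongest reply is that the sentence states its purpose and the parenthesis only glosses it. A looser reading, baseline at or below the titer that lies 4-fold under the ULOQ, gives 8.5 log2 or less, which is the correct set. A careful programmer may query the wording or silently put it right. That lowers the severity but does not rescue the text. The words describe distance from the ULOQ, and the protocol describes the opposite group in the same terms.

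It is also fair that little depends on this summary. It is descriptive and additional, and the SAP says that the secondary margins "are simply intended as benchmarks for unpowered comparisons". The ceiling is handled elsewhere for GMTs, through right-censoring and, in the comparison with UAM1, a baseline covariate. Those steps do not correct a seroconversion rate, but they mean that the plan does not ignore the ceiling.

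Three stronger inferences are tempting, and the documents do not support them:

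- **The rate would be near 0% for every vaccine.** This follows only with continuous titers, where no subject sits at exactly 8.5. The assay step is not given, and on a stepped scale that includes 8.5 the boundary subjects can seroconvert.
- **Every informative subject is excluded.** Those at exactly 8.5 log2 are kept.
- **The seroconversion comparison with UAM1 is itself wrong because it uses all subjects.** That follows the endpoint as the protocol defines it (Protocol 3.2), and nothing in the documents shows that the two studies differ in the share of baselines near the ULOQ.

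**Conclusion.** The definition is wrong as written. The inversion follows from the SAP's own limits and its 4-fold criterion, and it needs no distributional assumption. The only overlap between the literal and the correct subset is a baseline of exactly 8.5 log2.

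The size of the bias does rest on assumptions about baseline, rise and assay step. Across those examined, the literal rule gives 0% (continuous) or about 9% to 54% (stepped), against about 75% to 84% in the correct subset. The direction is downward in every case.

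Severity is low to moderate. A specified table would be misleading if programmed literally, but it is a supplementary descriptive summary of a secondary endpoint. The primary seroprotection non-inferiority test, the sample size, the type I error and the all-subject seroconversion results do not change.

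**What to change.** In SAP 6.6.1, replace the parenthesis with: baseline titer at least 4-fold below assay ULOQ, i.e. 8.5 log2 or less. This covers initially seronegative subjects and subjects at exactly 8.5, in all of whom seroconversion can be recorded.

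The cost is one phrase. SAP section 2 allows amendment before database lock, and no change to the protocol, data or sample size is needed.

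Optional, and separate from the correction: show the candidate-minus-UAM1 seroconversion difference in the corrected subset beside the all-subject difference. It would show whether baselines near the ULOQ influence the historical comparison. It is a new analysis that the SAP did not plan, and it costs one extra table.
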